6.5.12 Appropriateness of safety measurements

The safety assessments selected are standard for this indication and patient population. Ophthalmic evaluation has been included for detection of macular edema. Macular edema is an AE of special interest in patients treated with fingolimod because of the higher incidence seen in treated patients compared with active and placebo control groups in previous studies.

6.6 Other assessments

6.6.1 Health-related quality of life

Patients must complete the TSQM, questionnaires before other clinical assessments at any given visit. Completed questionnaires will be reviewed and examined by the investigator before the clinical examination for responses that may indicate potential AEs or SAEs. The investigator should review not only the responses to the questions in the questionnaires but also for any unsolicited comments written by the patient.

If the occurrence of AEs or SAEs is confirmed, the physician must record the events. Investigators should not encourage the patients to change the responses reported in the questionnaires.

6.6.1.1 Treatment Satisfaction Questionnaire for Medication v1.4 (TSQM v1.4)

Treatment Satisfaction Questionnaire for Medication (TSQM) was developed and validated as a general measure for treatment satisfaction (Atkinson 2004). The TSQM version 1.4 contains 14 items assessing the following 4 domains: Global Satisfaction, Effectiveness, Side Effects, and Convenience. This PRO must be completed prior to any other study visits assessments at the baseline, 6 and 12 month visits.

6.6.2 Resource utilization

Not applicable.

6.6.3 Pharmacogenetics/pharmacogenomics

Not applicable.

7 Safety monitoring

7.1 Adverse events

An AE is the appearance or worsening of any undesirable sign, symptom, or medical condition occurring after starting the study drug even if the event is not considered to be related to study drug. Study drug includes the investigational drug under evaluation and the comparator drug that is given during any phase of the study. Medical conditions and diseases present before starting study drug are only considered AEs if they worsen after starting study drug. Abnormal laboratory values or test results constitute AEs only if they induce clinical signs or symptoms, are considered clinically significant, or require therapy.

The occurrence of AEs should be sought by nondirective questioning of the patient at each visit during the study. Adverse events also may be detected when they are volunteered by the patient during or between visits or through physical examination, laboratory test, or other assessments. All AEs must be recorded in the AEs eCRF with the following information:

- 1. the severity grade (mild, moderate, or severe)
- 2. its relationship to the study drug(s) (suspected/not suspected)
- 3. its duration (start and end dates or if continuing at final examination)
- 4. whether it constitutes a serious AE (SAE)

An SAE is defined as an event which:

- is fatal or life threatening
- results in persistent or significant disability/incapacity
- constitutes a congenital anomaly/birth defect
- requires inpatient hospitalization or prolongation of existing hospitalization, unless hospitalization is for:
 - routine treatment or monitoring of the studied indication, not associated with any deterioration in condition
 - elective or preplanned treatment for a preexisting condition that is unrelated to the indication under study and has not worsened since the start of study drug
 - treatment on an emergency outpatient basis for an event not fulfilling any of the definitions of a SAE given above and not resulting in hospital admission
 - social reasons and respite care in the absence of any deterioration in the patient's general condition
- is medically significant, i.e., defined as an event that jeopardizes the patient or may require medical or surgical intervention to prevent one of the outcomes previously listed

Unlike routine safety assessments, SAEs are monitored continuously and have special reporting requirements (Section 7.2).

All AEs should be treated appropriately. Treatment may include one or more of the following: no action taken (i.e., further observation only); study drug dose adjusted/temporarily

interrupted; study drug permanently discontinued due to this AE; concomitant medication given; nondrug therapy given; or patient hospitalized/patient's hospitalization prolonged. The action taken to treat the AE should be recorded on the AE CRF.

For patients who experience an ischemic or thrombotic AE, specialist advice should be sought to determine diagnostic and therapeutic procedures. If a laboratory screen for coagulation abnormalities is deemed appropriate, it should include the following additional assessments: prothrombin time/partial thromboplastin time, homocysteine, activated protein C, lupus anticoagulant, antiphospholipid antibody, protein C, protein S, fibrinogen, and antithrombin III.

Patients who discontinue due to respiratory AEs should be evaluated by a pulmonary specialist and additional investigations (e.g., PFTs, chest x-ray or HRCT, biopsy) should be performed as needed.

Once an AE is detected, it should be followed until its resolution or until it is judged to be permanent, and assessment should be made at each visit (or more frequently, if necessary) of any changes in severity, the suspected relationship to the study drug, the interventions required to treat it, and the outcome. Sites should send all unscheduled laboratory samples to the central laboratory to ensure that the laboratory data are included in the clinical database and reported.

Information about common side effects already known about the investigational drug can be found in the investigator brochure or will be communicated between investigator brochure updates in the form of investigator notifications. This information will be included in the patient informed consent and should be discussed with the patient during the study as needed.

7.2 Serious adverse event reporting

To ensure patient safety, every SAE, regardless of suspected causality, occurring after the patient has provided informed consent and until 30 days after the patient has stopped study participation (defined as time of last dose of study drug taken or last visit whichever is later), must be reported to Novartis within 24 hours of learning of its occurrence.

Any SAEs experienced after this 30-day period should only be reported to Novartis if the investigator suspects a causal relationship to the study drug.

Recurrent episodes, complications, or progression of the initial SAE must be reported as follow-up to the original episode, regardless of when the event occurs. This report must be submitted within 24 hours of the investigator receiving the follow-up information. An SAE that is considered completely unrelated to a previously reported one should be reported separately as a new event.

Information about all SAEs is collected and recorded on the Serious Adverse Event Report Form. The investigator must assess the relationship of any SAE to study drug, complete the Serious Adverse Event Report Form in English, and send the completed, signed form by fax within 24 hours to the local Novartis Drug Safety and Epidemiology Department. The telephone and telecopy number of the contact persons in the local Clinical Safety and Epidemiology Department, specific to the site, are listed in the investigator folder provided to each site. The original copy of the SAE Report Form and the fax confirmation sheet must be kept with the CRF documentation at the study site.

Follow-up information is sent to the same person to whom the original Serious Adverse Event Report Form was sent, using a new Serious Adverse Event Report Form stating that this is a follow-up to the previously reported SAE and giving the date of the original report. The follow-up information should describe whether the event has resolved or continues, if and how it was treated, whether the blind was broken or not, and whether the patient continued or withdrew from study participation.

If the SAE is not previously documented in the investigator's brochure or package insert (new occurrence) and is thought to be related to the Novartis study drug, a Drug Safety and Epidemiology Department associate may urgently require further information from the investigator for health authority reporting. Novartis may need to issue an investigator notification to inform all investigators involved in any study with the same drug that this SAE has been reported. Suspected unexpected serious adverse reactions will be collected and reported to the competent authorities and relevant ethics committees in accordance with Directive 2001/20/EC or as per national regulatory requirements in participating countries.

7.2.1 Serious adverse event notification: multiple sclerosis relapse

Any MS relapses, as a general rule, should be reported on the relapse CRF instead of the AE/SAE forms. However, if, in the judgment of the investigator, any MS relapse is unusually severe and warrants specific notification, then an SAE Report Form must be completed and submitted according to SAE reporting procedures outlined above.

7.3 Pregnancies

To ensure patient safety, each pregnancy in a patient on study drug must be reported to Novartis within 24 hours of learning of its occurrence. The pregnancy should be followed up to determine outcome, including spontaneous or voluntary termination, details of the birth, and the presence or absence of any birth defects, congenital abnormalities, or maternal and/or newborn complications.

Pregnancy should be recorded on a Clinical Trial Pregnancy Form and reported by the investigator to the local Novartis Drug Safety and Epidemiology Department. Pregnancy follow-up should be recorded on the same form and should include an assessment of the possible relationship to the Novartis study drug of any pregnancy outcome. Any SAE experienced during pregnancy must be reported on the SAE Report Form.

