dose of fingolimod, macular edema, hypertension, dyspnea, bronchitis, and diarrhea. The AEs most prominently associated with fingolimod treatment (eg, liver enzyme elevations, bradycardia, and macular edema) appeared to show a dose response. There were no AEs that appeared to be specifically related to long-term treatment with fingolimod.

- In general, the AE profile of fingolimod in MS patients did not depend on gender, age, or previous treatment with disease-modifying drugs. The only exception was liver enzyme elevations, which were more frequent in male patients than in female patients treated with fingolimod.
- The overall incidence of infections, including serious infections, was similar in the fingolimod treatment groups and the comparator arms (IFN or placebo) in both completed Phase III studies. A slightly higher frequency of lower respiratory tract infections (primarily bronchitis) was observed in fingolimod-treated patients, with an apparent dose effect. The current data showed no clear relationship between lymphocyte count and the incidence of infections on fingolimod treatment.
- The accumulated data from the MS program do not show an association of fingolimod therapy with the development of malignancies. In the FREEDOMS study, more cancers were seen in the placebo group than in the treated groups. Incidence estimates for various forms of skin cancer (and other malignancies) from pooled safety data are comparable between treatment groups and placebo. There appears to be no increased risk with greater duration of exposure (Kappos et al., 2010).
- Initiation of fingolimod treatment has been associated with atrioventricular (AV) conduction delays usually as first-degree AV blocks (prolonged PR interval on electrocardiogram [ECG]). Second-degree AV blocks, usually Mobitz Type I (Wenckebach), have been observed in less than 0.5% of patients receiving fingolimod 0.5 mg in clinical trials. The conduction abnormalities typically were transient, asymptomatic, usually did not require treatment, and resolved within the first 24 hours on treatment.
- Data on the safe use of fingolimod in pregnancy or with breast-feeding are limited, although preclinical data suggest risk to the fetus and newborn is possible.

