 - history of substance abuse (drug or alcohol) in the past 5 years or any other factor (i.e., serious psychiatric condition) that may interfere with the patient's ability to cooperate and comply with the study procedures
 - progressive psychiatric/neurological condition that may affect participation in the study
- 20. Patients who have received an investigational drug or therapy within 180 days or 5 half-lives of randomization, whichever is longer.
- 21. Patients with a history of hypersensitivity to any of the study drugs, to drugs of similar chemical classes, or to mannitol.

- 22. Pregnant or nursing (lactating) women, where pregnancy is defined as the state of a female after conception and until the termination of gestation, confirmed by a positive human chorionic gonadotropin laboratory test.
- 23. Women of child-bearing potential, defined as all women physiologically capable of becoming pregnant, UNLESS they are using highly effective contraception during dosing with study treatment. Highly effective contraception includes:
 - Total abstinence (when this is in line with the preferred and usual lifestyle of the patient). Periodic abstinence (e.g., calendar, ovulation, symptothermal, post-ovulation methods) and withdrawal are not acceptable methods of contraception.
 - Female sterilization (have had surgical bilateral oophorectomy with or without hysterectomy) or tubal ligation at least 6 weeks before taking study treatment. In case of oophorectomy alone, only when the reproductive status of the woman has been confirmed by follow up hormone level assessment.
 - Male partner sterilization (at least 6 months prior to Screening). For female patients on the study, the vasectomized male partner should be the sole partner for that patient.
 - Use of oral, injected, or implanted hormonal methods of contraception or other forms of hormonal contraception that have comparable efficacy (failure rate <1%), for example, hormone vaginal ring or transdermal hormone contraception, placement of an intrauterine device or intrauterine system.

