5.5.9 Prohibited treatment

Use of the following treatments is NOT allowed after randomization:

- Immunosuppressive medication (e.g., cyclosporine, azathioprine, methotrexate, cyclophosphamide, mitoxantrone, cladribine)
- Other concomitant medications: immunoglobulins, monoclonal antibodies (including natalizumab), IFN beta, adrenocorticotropic hormone, other disease-modifying medications approved for MS including those approved subsequent to the start of this study

The administration of any live or live-attenuated vaccine (including for measles) is prohibited while patients are receiving fingolimod and for 8 weeks after fingolimod discontinuation.

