5.5.13 Early study termination

The study can be terminated at any time for any reason by Novartis. Should this be necessary, the patient should be seen as soon as possible and treated as described in Table 6-2 for a prematurely withdrawn patient. The investigator may be informed of additional procedures to be followed in order to ensure that adequate consideration is given to the protection of the patient's interests. The investigator will be responsible for informing the institutional review boards (IRBs) or independent ethics committees (IECs) of the early termination of the trial.

6 Visit schedule and assessments

The assessment schedule listing all assessments and visits to be performed under this protocol is provided in Table 6-1.

Starting at Visit 3, the visit window for all study visits is ± 5 days. Sites are encouraged to comply with this visit window as much as possible. Follow-up will occur within 3 months after the last dose of study drug for all patients (i.e., 3 months from the last study drug dose/EOT for patients who completed the study or 3 months from the last study drug dose for patients who were discontinued from the study). For any patients who permanently discontinue study drug early but decide to continue in the study, if the follow-up visit falls within the visit window for a scheduled visit, then assessments for both visits should be combined and completed. In addition to the scheduled visits, patients may have unscheduled visits following an onset of MS relapse or for other reasons as indicated in the protocol. All information should be collected per the unscheduled visit eCRF.

Table 6-1 Assessment schedule

Period	Screening	Treatment Period					FU ^a	
Visit	1	2	3	4	5	6	7/EOT	
Month	Day -45	Day 1	1	3	6	9	12	EOT
	to -1	Randomization						+3
Visit window (days)			±5	±5	±5	±5	±5	±5
Obtain informed consent	Х							
Background/demography	Х							
Inclusion/exclusion criteria	Х	X						
Medical history	Х							
MS history/MS treatment	Х							
Prior/concomitant medication	Х	X	Χ	Χ	Χ	Χ	Х	Х
Pregnancy test (serum)	Х							
Pregnancy test (urine dipstick)		X	Х	Χ	Χ	Χ	Х	Х
Physical examination	Х			Χ			Х	Х
Ophthalmologic examination ^b	Х			Χ	Х		Х	
Dermatology examination	Х						Х	
Randomization		Х						
Vital signs ^c /body weight	Х	Х	Χ	Χ	Χ	Χ	Х	Х
Pulmonary function tests	Х				Χ		Х	Х
12-lead electrocardiogram	Х	Χď					Х	
Blood chemistry and hematology	Х		Χ	Χ	Χ	Χ	Х	Х
Retrospective analysis blood sample	Х							
Serology	X							

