First-dose monitoring		X						
Urinalysis	Х	X	Х	Χ	Χ	Χ	Х	Х
Study drug dispensation		X	Х	Χ	Χ	Χ		
Study drug accountability			Χ	Χ	Х	Х	Х	
Magnetic resonance imaging	Х						Х	
EDSS	Х						Х	Х
MS relapse ^g	X	X	Χ	Χ	Χ	Χ	Χ	Χ
TSQM	X				Χ		Х	
C-SSRS	Х	X		Χ	Χ	Χ	Х	Χ
Adverse events/SAEs	X	X	Χ	Χ	Χ	Χ	X	Χ
Study completion form							X	

Abbreviations: C-SSRS=Columbia-Suicide Severity Rating Scale; ECG=electrocardiogram; EDSS=expanded disability status scale; EOT=end of treatment; FU=follow-up; HSV=herpes simplex virus; MS=multiple sclerosis;

; SAE=serious adverse event;

TSQM=treatment satisfaction questionnaire for medication.

- a. Follow-up will occur 3 months (12 weeks) after the last dose of study drug for all patients.
- b. The ophthalmology examination will include eye history, visual acuity, dilated ophthalmoscopy, and any procedures necessary to assess macular edema. Optical coherence tomography and fluorescein angiography will be done only if needed to confirm macular edema.
- c. Body temperature is collected only at Screening, Visit 7/EOT, and at the follow-up visit.
- d. A 12-lead ECG will be performed before fingolimod and glatiramer acetate administration, and 6 hours after the fingolimod administration only.

e. Patients will be tested for human immunodeficiency virus, varicella zoster virus (as per guidance in Appendix 3), HSV-1, HSV-2, and rubeola virus.

g. Patients should report symptoms indicative of a relapse at a scheduled visit or at any other time and will be instructed to immediately contact the treating physician if they develop new or reoccurring or worsening neurological symptoms. A neurological examination by the independent evaluating physician must be arranged as soon as possible, preferably within 7 days of the onset of symptoms.

Table 6-2 Abbreviated schedule of assessments for patients who discontinue study drug

Period	Off-Treatment						
Visit	5	6	7/EOS				
Month	6	9	12				
Visit window (days)	±5	±5	±5				
MS relapses ^a	Х	Х	Х				
MS treatment/steroids	Х	Х	Х				
Concomitant medications	X	Х	X				
Magnetic Resonance Imaging							
EDSS			X				
TSQM			X				
		.,					
C-SSRS	X	X	X				
Physical exam	X		X				
Ophthalmologic exam ^c			X				
Dermatology examination			X				
Vital signs ^d /body weight	X	X	X				
Pulmonary function tests			X				
Laboratory values	Xe	Xe	Х				
Adverse events	X	X	X				
SAE reporting	Х	Х					

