6.5.6 Pregnancy and assessments of fertility

Serum pregnancy test will be performed for all women by the central laboratory as detailed in Table 6-1. Patients becoming pregnant will be recommended to interrupt the study drug. Additional pregnancy testing may be performed at the investigator's discretion during the study.

Confidential

Novartis

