#### 3.8.5 Safety data cutoff and visit windows for summaries on follow-up set

For safety summaries on the safety set, only data which are within 45 days (5 times the half life of FTY720, 9 days) after the last dose of study drug will be considered.

For safety summaries on the follow-up set, all data (including assessments or events more than 45 days after the last dose of study drug) will be considered.

The visit windows below will be used in summaries on the follow-up set.

- 1) Last assessment on study drug
- 2) Day 1 to 45 after study drug discontinuation

- 3) Month 3 (day 46 to 135) after study drug discontinuation
- 4) Month 6 (day 136 to 270) after study drug discontinuation
- 5) Month 12 (day 271 to 540) after study drug discontinuation

For the visit window 1), last assessment on or before the last dose date will be used. For visit windows 2) to 5), assessments collected during the specified day intervals after the last dose date will be used.

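### Neither the contraception rule nor the 24-hour pregnancy report has a post-dose period, although fingolimod remains in the body for weeks after the last capsule

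*Protocol*

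**What the plan says.** **Reporting.** The first sentence of Protocol 7.3 requires that "each pregnancy in a patient on study drug must be reported to Novartis within 24 hours of learning of its occurrence". The second paragraph of 7.3 then asks the investigator to put the pregnancy on the trial pregnancy form and report it to the sponsor's safety department. That paragraph has no on-drug limit and states no deadline. It also makes any SAE during pregnancy reportable on the SAE form.

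**Contraception.** Exclusion criterion 23 (Protocol 4.2) excludes women of child-bearing potential "UNLESS they are using highly effective contraception during dosing with study treatment".

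**Action on pregnancy.** Protocol 6.5.6 gives one instruction: "Patients becoming pregnant will be recommended to interrupt the study drug".

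**Exposure and risk.** Protocol 1.1 states that "preclinical data suggest risk to the fetus and newborn is possible" and that pregnancy data are limited. SAP 3.8.5 limits safety-set summaries to data "within 45 days (5 times the half life of FTY720, 9 days) after the last dose of study drug". For live vaccines, Protocol 5.5.9 does set a post-dose period: administration "is prohibited while patients are receiving fingolimod and for 8 weeks after fingolimod discontinuation".

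**Detection.** Table 6-1 schedules a urine pregnancy test through Month 12 and again at the follow-up visit. Its footnote a fixes the timing: "Follow-up will occur 3 months (12 weeks) after the last dose of study drug for all patients".

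**SAE cover.** Section 7.1 counts a congenital anomaly as an SAE. Section 7.2 requires every SAE until 30 days after the later of last dose and last visit, and after that only where causality is suspected.

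**The concern.** The contraception wording and the 24-hour wording both stop at the last dose, but drug exposure does not. The protocol treats being on drug and being in the study as different states. The glossary separates study drug discontinuation from premature withdrawal, and 5.5.10 keeps patients who stop drug in the study. Post-dose periods are written elsewhere (live vaccines, SAEs), so a site could take the silence here as deliberate.

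Two things are at stake. On the visible text, a participant could stop contraception with her last capsule and conceive while drug is still present, without departing from any stated rule. And every patient tested at the 12-week follow-up has already stopped study drug. A positive result there is the foreseeable case, and 7.3 does not say whether the 24-hour duty applies. Sites could handle the same result differently, in a setting where the protocol itself says pregnancy data are limited.

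**Working it through.** **1. The plan's own figure.** SAP 3.8.5 gives a half-life of 9 days and a cutoff of five half-lives: 5 × 9 = 45 days. This reproduces.

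**2. Drug remaining after the last dose.** Assuming simple exponential decline, the fraction remaining at day d is 0.5^(d/9).

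| Day after last dose | Calculation | Remaining |
|---|---|---|
| 15 | 0.5^(15/9) | 31% |
| 30 | 0.5^(30/9) | 9.9% |
| 45 (SAP cutoff) | 0.5^5 | 3.1% |
| 56 (8-week vaccine rule) | 0.5^(56/9) | 1.3% |
| 84 (12-week follow-up) | 0.5^(84/9) | 0.16% |

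**3. Does the existing test suit such a period?** Follow-up is at 12 × 7 = 84 days. With a 45-day period, the latest conception falls 84 − 45 = 39 days before the test. With 56 days it falls 84 − 56 = 28 days before. Assuming the dipstick is reliable at those intervals, no extra test is needed.

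**4. How far does SAE cover reach?** If the follow-up visit is the last visit, unconditional SAE reporting runs to about 84 + 30 = 114 days after the last dose. Assuming birth about 38 weeks (266 days) after conception, a term birth from a conception on day 0 to 45 falls on about day 266 to 311. A defect first found at birth would then be reportable under 7.2 only if the investigator suspects causality. Patients who stop drug early but attend later visits have longer cover.

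**5. The reporting texts side by side.**
- 7.3, first sentence: mandatory, 24 hours, worded for patients on drug.
- 7.3, second paragraph: report and record, no on-drug limit, no stated deadline.
- 7.1 and 7.2: serious outcomes, but not an uneventful pregnancy.

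A post-dose pregnancy is therefore reportable on a natural reading. Whether it must be reported within 24 hours is not stated.

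**6. How many pregnancies?** The documents do not say. SAP section 10 gives 370 + 352 = 722 fingolimod patients. For scale only, assume that 40% to 70% are women of child-bearing potential and that 1% to 5% of them conceive per year after stopping.
- 45 days: 0.40 × 722 × 0.01 × 45/365.25 = 0.36, to 0.70 × 722 × 0.05 × 45/365.25 = 3.11.
- 56 days, same formula: 0.44 to 3.87.

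Both percentages are assumptions without a source in the documents. They do not model women who stop contraception specifically in order to conceive.

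**The case against.** The strongest reply is that the protocol already deals with these pregnancies. The second paragraph of 7.3 covers pregnancy without an on-drug limit and asks for an assessment of any outcome's relationship to study drug. A test scheduled 12 weeks after dosing makes most sense if a positive result is acted on. The SAE rules pick up serious outcomes, with no time limit where causality is suspected. Outcome follow-up is phrased as a recommendation even for on-drug pregnancies, so little should hang on the difference between must and should. This largely stands. A reader might infer that post-dose pregnancies go unreported; the documents do not support that. What survives is the missing statement about the 24-hour duty.

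The second reply is that contraception advice may sit in documents not available here. The consent form is separate (Protocol 10.2), as are the patient leaflet (5.5.4), the investigator brochure (7.1) and local prescribing information (5.5.5). Section 6.5.7 cannot be read in the public copy. This stands as a limit. One cannot infer that participants were told they could stop contraception at the last dose, only that criterion 23 and 6.5.6 set no later date.

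Third, the benchmarks are borrowed: 45 days is an analysis cutoff applied to all arms, and 8 weeks concerns live vaccines. That is fair. Neither is a fetal-safety period, and no document ties a residual drug level to fetal harm. They serve only as guides to how long exposure lasts.

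**Conclusion.** The point holds as a low-cost safety improvement. The visible contraception requirement ends with dosing, when on the documents' own half-life about 10% of drug would remain a month later and 3% at 45 days. That rests on exponential decline and on no longer period being stated in the unseen documents. On reporting, the gap is confined to whether the 24-hour duty covers a pregnancy conceived or found after the last dose. The number of pregnancies concerned is unknown and likely small: between about 0.4 and 4 on the assumed ranges, and the documents cannot show that any would be missed. The primary analysis and its power are not affected.

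**What to change.** For fingolimod patients:

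- **6.5.6 and criterion 23:** state that highly effective contraception continues through dosing and for at least 45 days after the last dose. A 56-day period would match the vaccine rule; the sponsor's safety group should choose. The instruction belongs in 6.5.6 as well because Protocol section 4 has eligibility assessed only at screening and randomization. Check the period against the consent form and prescribing information, and align them.
- **7.3:** extend the 24-hour sentence to pregnancies with an estimated conception date within that period after the last fingolimod dose, and say that this includes one found at the follow-up visit. Say also that such a pregnancy goes on the existing form and is followed to outcome.

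The cost is a few lines of text and a site update. The urine test and pregnancy form already exist. The downside is a few more forms, outcome follow-up beyond the last visit, and a consent update if the consent form is silent.
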